## **7 SAFETY ASSESSMENTS**

### **7.1 Specification of Safety Parameters**

There are minimal safety concerns associated with this intervention. While nurse care managers who participate in the training may change the way they interact with patients and caregivers, all clinical and patient management decisions will remain in the RN, PCP and other care providers’ hands. Our investigative team includes that medical director of the iCMP program. Although we do not anticipate safety issues, if nurses do identify issues that are prompted by the training, we will work with the iCMP team to update nurses or advise them of the issues.

The major risks to caregivers of PWD will be discomfort related to the survey questions. We will inform caregivers that they can refuse to answer any questions and can terminate their participation at any time. We will also inform caregivers that refusal to answer any questions will not have any impact on the care they are receiving.

## **8 INTERVENTION DISCONTINUATION**

We will not specify criteria for discontinuation of the intervention for this pilot study.

## **9 STATISTICAL CONSIDERATIONS**

### **9.1 General Design Issues**

The primary purpose of this pilot is to assess feasibility of collecting the primary clinical outcome, defined as emergency department visits among the PWD. Secondary outcomes will assess the feasibility of implementation, number of contacts between nurse care managers and care partners, and documented advance care planning.

### **9.2 Sample Size**

Given limitations to the trial duration, this study is considered a pilot to understand the feasibility of measurement and to provide data to support calculation of effect sizes for a subsequent full-scale study if the initial pilot results appear promising.

### **9.3 Outcomes**

The primary outcome for the is pilot is emergency room visits within 6 months. We will rely on Epic and Medicare claims data for all measures of healthcare service utilization and costs, care intensity / quality, documentation of advance care planning, and documentation of medication review. These outcomes will be assessed for all PWD who are cared for by selected nurse care managers using retrospective analysis of existing health care data. We anticipate that this will include 150 PWD among care managers who receive early training and 150 PWD who receive delayed training. These data are housed in an existing data repository; we anticipate minimal missing data. Key secondary outcomes will assess the number of contacts between nurse care managers and care partners, and documented advance care planning; these measures likewise available from the existing data warehouse and we anticipate minimal missing data.

In order to ensure systematic capture of key clinical outcomes within this pilot, we will survey caregivers of PWD receiving care management from the 30 selected nurse care managers and meeting our inclusion and exclusion criteria at months 3 and 9. We expect that a minimum of 50% of caregivers will complete each survey, yielding an expected sample of 75 PWD caregiver respondents completing each survey and 37 PWD caregiver respondents completing both an initial and follow- up survey for nurses assigned to the early and the delayed training. We will assess the completeness and correlation of behavioral symptoms of dementia, caregiver depression, caregiver burden, and PWD quality of life captured via trained nurse care managers (and documented in Epic or iCMP data) with caregiver survey responses.

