## **6 STUDY PROCEDURES**

There will be five sources of data to be used in these analyses.

- iCMP Program Data: iCMP collects key process measures including patient status within the program, the number of nurse care manager contacts with the patient / caregiver and community resource requests. Nurses can document caregiver strain and PWD behavioral symptoms in structured fields or in iCMP visit notes. Caregiver depression can likewise be assessed and documented in iCMP visit notes. These data will be used to measure iCMP visit frequency and documentation of key patient and caregiver outcomes in order to assess CareEco implementation fidelity. iCMP program data is captured within Epic and flows directly into the Partners data warehouse, where it is co-housed with clinical and financial data from the Partners electronic health record (Epic) and linked claims data for patients in the Medicare MSSP contract.
- Medicare Claims data will be used to identify iCMP patients with dementia at baseline and over time, and to construct measures of health care utilization and costs.
- Epic clinical data will be used to identify patient caregivers, capture PWD and caregiver outcomes documented in the iCMP note, and identify whether medication reconciliation and serious illness conversations / advance care planning occurred related to the iCMP interaction. In addition, Epic contains structured assessments of caregiver strain and PWD behavioral symptoms. All Epic elements flow to tables within the Partners data warehouse.

For some PWD, outcome measures of caregiver strain and PWD behavioral symptoms have already been integrated into Epic documentation (see data sources above). We will compare EMR-integrated measures with measures derived from the surveys of PWD caregivers to determine the relative completeness and quality of the two data sources with a goal of reducing more resource-intensive primary data collection in future studies.

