Interviews will be scheduled two months after the launch of the CareEco training (month five). These interviews will be conducted in care manager offices or by telephone or a video technology platform at the convenience of the care manager. The interviews will last approximately 30 to 40 minutes. Research with the iCMP care management staff, conducted by our team in both 2017 and 2018 as part of a PCORI funded study of care management programs, achieved 75% participation rates. Interview domains will include 1) general experience in caring for PWD and their caregivers; 2) experience in direct outreach to caregivers and patients (including identifying the most knowledgeable or engaged caregivers); 3) perceptions of services most needed and most difficult to arrange for patients with dementia and their caregivers; 4) assessment of the adequacy of training as adapted to the iCMP context; 5) recommendations for further adaptation of the CareEco model, and 6) among care managers not participating in the training, implementation

barriers, including contextual factors, fit and overarching issues that impacted non-participation.

The following table summarizes the measures that will be used in this study.

Variable	Source	Primary or secondary outcome	Description
ED visits	Medicare Claims data	Primary	ED visits per member per month over 6 months; Feasibility of collection (Primary objective), difference between early and delayed cohorts (secondary objective)
Service utilization and costs	Medicare Claims data	Secondary	Hospitalizations, Observation stays, urgent visits, total medical expense; Feasibility of collection (Primary objective), difference between early and delayed cohorts (secondary objective)
Documentation of advance care planning	Epic	Secondary	
Documentation of medication review and reconciliation	Epic	Secondary	
Caregiver Depression *	Caregiver survey	Primary and Secondary	PHQ-8 (8 item)
Caregiver strain and burden *	Epic	Primary and Secondary	Caregiver Strain Index presence in Epic and magnitude
Caregiver strain and burden *	Caregiver survey	Primary and Secondary	Zarit Rating Scale (12-item) 
Behavioral Symptoms of Dementia *	Epic and Caregiver survey	Primary and Secondary	NPI-Q (Neuropsychiatric inventory Questionnaire)  presence in Epic and magnitude
PWD quality of life	Caregiver survey	Secondary	QOL-AD (13 items) 

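### The Epic-versus-survey comparison names completeness and correlation but no measure of agreement, so it cannot show whether recorded Epic scores run systematically low or high

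*Protocol*

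**What the plan says.** Protocol 9.3 (Outcomes) sets out the comparison: "We will assess the completeness and correlation of behavioral symptoms of dementia, caregiver depression, caregiver burden, and PWD quality of life" as "captured via trained nurse care managers (and documented in Epic or iCMP data) with caregiver survey responses". Protocol section 6 (Study Procedures) describes what appears to be the same exercise in other terms. The two sources will be compared "to determine the relative completeness and quality of the two data sources", "with a goal of reducing more resource-intensive primary data collection in future studies". Quality is not defined.

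The measures table in section 6 shows which instruments are available:

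- **Behavioral symptoms:** the NPI-Q, listed for both Epic and the survey, with "presence in Epic and magnitude".
- **Caregiver burden:** for Epic, "Caregiver Strain Index presence in Epic and magnitude"; for the survey, the 12-item Zarit. The survey battery in section 6.2.2 lists the Caregiver Strain Index and not the Zarit.
- **Caregiver depression and patient quality of life:** the PHQ-8 and QOL-AD, each with the survey as its only listed source. Section 6 says depression may be documented in visit notes but names no instrument.

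Neither document gives an agreement statistic, a correlation threshold or a rule for relying on Epic. The SAP does not describe the comparison.

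**The concern.** Relying on one source in place of another requires that their values agree in scale units. Correlation answers a narrower question: whether the two sources order people alike along a line. It is the only statistic the plan names for comparing recorded values, and it cannot register a constant or proportional shortfall. Completeness does not fill the gap, because a score recorded too low still counts as recorded.

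A systematic difference is plausible here because the recorders differ. Epic values come from nurse care managers, who know whether they have been trained (Protocol 5.2) and who deliver the intervention. Survey values come from interviewers unaware of training status (Protocol 10.1). If training changes how nurses score, an Epic-based outcome in a later trial could differ by arm for recording reasons alone. At stake is the advice this pilot gives on how the full-scale study should collect these outcomes.

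**Working it through.** **1. The plan's own figures.** 30 nurses × 10 PWD / 2 = 150 per arm. 150 × 0.50 = 75 respondents per survey. 150 × 0.50 × 0.50 = 37.5, stated as 37, which implies that response to the two surveys is independent. These reproduce. The plan gives no target or sample size for the Epic-survey comparison.

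**2. Constant shortfall.** Pearson's r = cov(X, Y) / (SD_X × SD_Y), so subtracting d from every Y leaves it unchanged. Lin's concordance with equal SDs s is 2rs² / (2s² + d²). The documents give neither r nor s; assume r = 0.80 and s = 6 or 10.

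| Epic shortfall d | r | Concordance, s = 6 | Concordance, s = 10 |
|---|---|---|---|
| 0 | 0.80 | 0.80 | 0.80 |
| 2 | 0.80 | 57.6/76 = 0.76 | 160/204 = 0.78 |
| 4 | 0.80 | 57.6/88 = 0.65 | 160/216 = 0.74 |

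**3. Proportional shortfall.** If Epic = 0.7 × survey with an assumed survey mean of 15, r = 1.00 and the mean shortfall is 0.3 × 15 = 4.5 points.

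**4. What a paired difference could show.** SD_diff = s√(2(1 − r)). The 95% CI half-width is t × SD_diff / √n, with t = 1.99 for 75 pairs and 2.03 for 37. The limits of agreement are the mean difference ± 1.96 × SD_diff. I take 75 pairs as one arm's respondents to one survey if all have an Epic score, and 37 as the case where about half do. Clustering by nurse is ignored here and could widen the intervals.

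| s | r | SD_diff | Half-width, 75 pairs | Half-width, 37 pairs | Limits of agreement |
|---|---|---|---|---|---|
| 6 | 0.6 | 5.37 | 1.23 | 1.79 | ±10.5 |
| 6 | 0.8 | 3.79 | 0.87 | 1.27 | ±7.4 |
| 6 | 0.9 | 2.68 | 0.62 | 0.89 | ±5.3 |
| 10 | 0.6 | 8.94 | 2.06 | 2.98 | ±17.5 |
| 10 | 0.8 | 6.32 | 1.46 | 2.11 | ±12.4 |
| 10 | 0.9 | 4.47 | 1.03 | 1.49 | ±8.8 |

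An observed 2-point mean difference would have a CI excluding zero in 9 of the 12 cells.

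**5. Whether a ±2-point acceptance rule would work.** Assume SD_diff = 4.8 and no true bias. The chance that the whole CI lies within ±2 is about 2Φ((2 − half-width)/SE) − 1.

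- 75 pairs: SE 0.55, half-width 1.10, chance about 89%.
- 37 pairs: SE 0.79, half-width 1.60, chance about 39%.

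With 37 pairs, such a rule would more often than not fail a source with no bias.

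**The case against.** The strongest reply is that this is an exploratory comparison in a pilot and that nothing is decided by it. Much of that stands.

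- A reader might infer that Protocol 9.3 decides whether Epic replaces the survey. It does not. It contains no threshold or rule, and section 6 speaks of reducing primary data collection in future studies.
- Completeness is a named criterion and would expose scores never entered. What remains is bias among recorded values.
- A reader might infer that Epic reads several points low. The documents give no Epic-survey difference, and the shortfalls above are assumed.
- It is tempting to measure bias against the 2 points in SAP 8.2. That figure concerns NPI-Q Distress and is applied there to a between-arm difference-in-differences. A shortfall equal across arms and times cancels from that estimate; a proportional one, say Epic = 0.6 × survey, would shrink a 2-point effect to 1.2. Moreover, only the survey NPI-Q is said to include caregiver distress (section 6.2.2), and Epic may not hold that subscale.
- Only the NPI-Q is clearly listed for both sources. Raw differences between the Strain Index and the Zarit have no meaning, and correlation is a fair descriptor there.

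None of this answers the central point: for the NPI-Q, the named statistics cannot show a level difference, although the plan collects magnitude on the same instrument in both sources.

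**Conclusion.** The concern holds in a limited form. The plan aims to judge the relative quality of two sources, yet the only statistic it names for recorded values is blind to systematic under- or over-scoring. That is a mathematical property of correlation and needs no assumption. The size of any bias is unknown. The precision figures rest on assumed SDs of 6 to 10 and correlations of 0.6 to 0.9, which give half-widths of 0.62 to 2.06 points with 75 pairs and 0.89 to 2.98 with 37. The pair counts are also optimistic: section 6 says the measures are in Epic for only some PWD, and Protocol 9.3 refers to values captured by trained nurses. The documents do not support saying that the survey will be dropped or that Epic is known to be biased. Severity is low: the ED-visit outcome and the survey-based NPI-Q Distress analysis do not depend on this comparison.

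**What to change.** In Protocol 9.3, name the criteria as completeness, correlation and, where the same instrument is in both sources, agreement. Then:

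- For the NPI-Q, report the mean paired Epic-minus-survey difference with a 95% CI that allows for clustering by nurse, and 95% limits of agreement. Use whichever subscale both sources hold, in pairs recorded within a stated window, overall and by arm where data allow.
- Report the result as an estimate, and as inconclusive if the CI is wide. Do not set a ±2-point pass/fail rule.
- Keep correlation as description only where instruments differ or no Epic instrument is listed. Draw no conclusion about relying on Epic from correlation alone.
- Define quality in section 6, and say whether records from nurses not yet trained enter the comparison.
- Reconcile the survey burden instrument between the measures table (Zarit) and section 6.2.2 (Caregiver Strain Index). If the Strain Index is in both sources, the same agreement analysis applies.

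The cost is a few sentences and slightly more analysis, with no new data collection. The window will remove some pairs, and the verdict on Epic data may be less favourable than a correlation would suggest.

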### **9.4 Data Analyses**

Depending on the type of outcome, we will conduct either a linear, negative binomial, or logistic regression, with random effects for nurses, to account for multiple patients nested within the same nurse. The primary predictor will be intervention (iCMP nurse care manager assignment to early CareEco training versus delayed training). Models will be adjusted for a limited number of baseline covariates: dementia stage and severity; Elixhauser score; and patient characteristics. If there are many unbalanced patient or

nurse characteristics, we will use propensity score weighting to adjust for confounding in the face of the limited sample size. Secondary models will examine process measures as potential mediators of the intervention effect on reported outcomes, clinical outcomes, and utilization outcomes. Subgroup analyses will be explored, but given the limited sample size, we do not expect sufficient power to detect effect modification nor significant intervention effects within subgroups.

## **10 DATA COLLECTION AND QUALITY ASSURANCE**

### **10.1 Data Collection Forms**

Primary data collection for PWD and caregivers will include multiple patient-level clinical and claims measures drawn from system records as well as telephone surveys conducted with caregivers of PWD at baseline and follow up. Survey interviewers will be supervised by [name] and will not be aware of whether the PDW's nurse care manager has undergone CareEco training. Data for all patients and caregivers will be maintained in RedCAP; survey data will be entered directly into RedCAP using standard survey procedures. Interviewers will maintain a record of all attempted contacts (Call Log) and their outcomes; a final disposition for each attempted case will be determined when all efforts are exhausted.

### **10.2 Data Management**

RedCAP tools for data management include a participant list, a PWD/Caregiver list, a patient/caregiver baseline and follow up survey tools

### **10.3 Quality Assurance**

#### **10.3.1 Training**

Training of nurse care managers will be standardized and based on task force feedback gathered in the first two months of the study.

#### **10.3.2 Quality Control Committee**

If there is a study quality control committee, describe membership and list the reports that they review.

#### **10.3.3 Metrics**

Provide quality control metrics for outcome measures.

#### **10.3.4 Protocol Deviations**

The team will hold weekly meetings to discuss study progress, including any necessary adaptations that require IRB review. A LabArchives record will be created for the project and linked to RedCAP documents and workflows. Using this approach, protocol deviations can be identified and reported promptly.

### 10.3.5 Monitoring

PI, Co-PIs, and Project Manager will ensure proper monitoring and tracking of all pilot data, records, and forms. All identifiable data will be secured on password protected Partners Healthcare system computers or locked file cabinets. All data will be de-identified as soon as practically possible. Regularly scheduled meetings (2 times per month) will be used to track progress and ensure compliance with study protocols. The study team will have established protocol and workflow to communicate with clinical teams in real time if patient safety issues are identified that need immediate attention.

## 11 **PARTICIPANT RIGHTS AND CONFIDENTIALITY**

### 11.1 Institutional Review Board (IRB) Review

This protocol and any subsequent modifications will be reviewed and approved by the IRB or ethics committee responsible for oversight of the study.

### 11.2 Informed Consent Forms

Nurse care manager participation in training is a quality improvement project and therefore consent is not applicable.

For PWD and caregivers, completion of the survey does not generally require a consent form, rather the elements of consent are in the advance letter and are confirmed in the telephone interview. Completion of the survey implies consent, no additional consent forms will be signed by PWD or their caregivers.

### 11.3 Participant Confidentiality

Any data, forms, reports, video recordings, and other records that leave the site will be identified only by a participant identification number (Participant ID, PID) to maintain confidentiality. All records will be kept in a locked file cabinet. Recordings will be saved for the duration of the pilot, and transcripts will be saved for seven years. All computer entry and networking programs will be done using PIDs only. Information will not be released without written permission of the participant, except as necessary for monitoring by IRB, the FDA, the NIA, and the OHRP.

### 11.4 Study Discontinuation

The study may be discontinued at any time by the IRB, the NIA, the OHRP, or other government agencies as part of their duties to ensure that research participants are protected.

## 12 **ETHICAL CONSIDERATIONS**

Include in this section the guiding ethical principles being followed by the study. If the study is conducted at international sites, consider including reference to the Declaration of Helsinki, CIOMS, International Ethical Guidelines for Biomedical Research Involving

Human Subjects (2002), or another country's ethical policy statement, whichever provides the most protection to human subjects.

### **13 PUBLICATION OF RESEARCH FINDINGS**

Publication of the results of this trial will be governed by the policies and procedures developed by the Steering Committee. Any presentation, abstract, or manuscript will be made available for review by the sponsor and the NIA prior to submission.

1 INTRODUCTION

The prevalence of Alzheimer's Disease (AD) and related dementias, currently affecting 5.8 million Americans, is expected to increase to 14 million by the year 2050, with annual costs escalating from \$290 billion to \$1.1 trillion. Dementia adversely impacts caregivers, who provide 16 million hours of unpaid care per year for individuals with AD and related dementias, and suffer greatly from stress, depression, anxiety, and health problems, which often leads to poor outcomes for their loved ones with dementia. Primary care physicians report a lack of time, training and resources to systematically screen for, diagnose, and treat dementia, as well as to provide adequate psychosocial support to unpaid caregivers^{5,6}. This may lead to inadequate advance care planning and contribute to avoidable ED visits, hospital admissions and medical interventions as the disease progresses. Prior studies have demonstrated that enrollment in a collaborative care program for dementia is associated with improved functioning and quality of life, reduction in behavioral symptoms of dementia and a decrease in caregiver burden with a net cost savings as high as \$2800 annually per patient⁷. Many of these programs are, however, resource intensive, requiring the creation of new clinical teams embedded in primary care settings. Recently, a telephone-based collaborative dementia care intervention (Care Ecosystem), that provides personalized support and standardized education through care plan protocols⁸ delivered by trained health care navigators, has demonstrated lower rates of ED utilization and reduced caregiver depression and burden⁹.

The Care Ecosystem (CareEco) model uses a telephone-based intervention to support persons with dementia (PWDs) and their caregivers, screening for common dementia-related problems and providing modular standardized support protocols and caregiver education. Specially trained health care navigators systematically identify needs and address health status, advance care planning, medication management and management of challenging behaviors. Health care navigators receive backup support from a nurse, social worker, dementia specialist, and pharmacist, and maintain close communication with the primary care provider of the PWD. CareEco was found to reduce ED utilization, improve PWD quality of life and improve caregiver outcomes⁹. While the healthcare navigators used in CareEco offer clear value, this model, if adopted in a system with established, robust care management teams and no preexisting health care navigators, could actually increase cost by adding personnel in the setting of limited space and resources. We hypothesize that adapting the CareEco model to augment the dementia care provided by a pre-existing care management team could improve care manager self-efficacy in supporting PWDs, improve outcomes for PWDs and their caregivers, and optimize sustainability by enhancing dementia care competency of existing clinicians. In this pragmatic clinical trial pilot, we developed and tested an adapted form of the CareEco intervention with experienced Integrated Care Management Program (iCMP) nurse care managers engaged in the care of high-risk, high-cost PWD in a large health system.

The integrated care management program (iCMP) within Mass General Brigham is a nurse-led longitudinal care management program embedded in Primary Care practices across the Mass General Brigham network that provides care management support to the most medically complex and seriously ill patients. iCMP care managers assess each patient to clarify problems, identify barriers to accessing clinical care and community-based services, including the social determinants of health, and create a patient-centric care plan. The iCMP program serves all payor populations and has cared for over 38,000 patients since 2012. Approximately 14,000 patients are presently enrolled in iCMP, 64% of whom are Medicare beneficiaries. An independent evaluation of Medicare patients in iCMP, relying on 18 months of claims data post-iCMP assessment, found an average savings in total medical expense (TME) of \$101 per member per month¹⁰. iCMP teams care for many patients with dementia, but are not specifically trained in the care of persons

with dementia (PWD) and their caregivers. iCMP care managers have described lower levels of self-efficacy in the care of PWD. An analysis of cognitive disorders within the Mass General Brigham system identified a conservative estimate of dementia prevalence of 8.8% among iCMP Medicare patients based on ICD-10 diagnosis codes for dementia, as compared to a roughly 5.1% prevalence of dementia among all Medicare patients. Thus, the iCMP program provides an opportunity to train nurse care managers in an adapted CareEco model for dementia patients.

